6.1 Overview of protocol

The clinical evaluation will be conducted at three (3) clinical sites, on three (3) separate testing systems. In total, at least three (3) lots of test kits will be used in the evaluation; approximately equal numbers of samples will be tested on each of the three lots.

For concordance evaluation, approximately 585 samples from oral lesions and 495 samples from genital lesions will be tested. The study will use residual samples collected for clinical testing from patients with clinical evidence of HSV1/2 infection. The sample size is based on prevalence of HSV1 and HSV2 in oral and genital swabs.

If required, due to low prevalence, the clinical sample set may be enriched with contrived positive samples where virus is spiked into either negative clinical matrix or VTM.

6.2 Assay validation

6.2.1 Familiarization

Familiarization testing is done to ensure that personnel at the clinical sites who will be performing the assay are appropriately trained. When a clinical site is initiated, a panel of 5 samples will be assayed in 4 replicates on the same day by one technician at each site. The sponsor will provide this sample panel and the expected result ranges. The sponsor will review the results; if the panel samples fall within the expected result ranges, the personnel at that site may proceed to assay the precision/reproducibility samples using the *Sentosa*[®] HSV1/2 Qualitative PCR testing system and the reference assay.

6.2.2 Precision and reproducibility

Precision and reproducibility will be evaluated with 3 lots of *Sentosa* SA HSV1/2 Qualitative PCR test kits; all lots will be used at all sites to evaluate lot-to-lot variation. The blinded Precision/Reproducibility Test Panel includes negative and positive quality control materials and a Precision/Reproducibility Sample Panel containing the following:

- a negative sample
- 1.5xLoD HSV1;

- 1.5xLoD HSV2;
- 3xLoD HSV1; and
- 3xLoDHSV2.

This sample panel plus the quality control materials will be run 20 times at each site.

Samples in this Precision/Reproducibility Sample Panel will not be assayed using the reference assay. Each sample (positive and negative samples) will be tested in replicates of 3 and each control (positive control and negative control) will be tested in replicates of 2 in one run and two runs will be carried out daily over 5 days (total test points per sample: 3 replicates x 1 run/day/operator x 2 operators x 5 days x 3 sites = 90). Intra-assay reproducibility will be calculated for within-run values. Between-day, between-run, between-lot, between-operator and between-site variance, as well as total variance, will be calculated. Statistical analysis will be done following the CLSI EP5-A2 guideline. Refer to protocol PL-457 for more details. Protocol PL-457 may be found in the appendix.

6.2.3 Concordance

For concordance testing, a minimum of 585 oral samples and 495 genital samples will be collected at 3 clinical sites. Each site will test at least 195 oral samples and 165 genital samples.

Samples will be tested using the investigational device and the reference assay in parallel (testing initiated on the same day from the same sample) by a qualified technician who has been specifically trained to participate in the study. Results will be sent to the study manager for review; the clinical site will be notified if any samples must be retested. Residual sample may be stored after initial testing following storage requirements in section 5.4 until retest notification has been received.

Samples that yield discordant results between the investigational and reference methods will be re-tested by Vela Research USA, using different PCR primers and bidirectional sequencing. Results from discrepant testing will be reported as a footnote in the package insert. Only samples containing sufficient volume will be retested for discrepant analysis.

Any sample left after all testing is completed should be frozen at -70°C for shipment to Vela Research USA.

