4.1 Materials supplied by the sponsor

Vela Research USA will supply the following reagents and equipment and its associated software to each testing site:

- Sentosa SX101 instrument for extraction and PCR set-up;
- Sentosa SA201 for real time nucleic acid amplification and detection;
- Sentosa Link software:
- Sentosa SA201 Series software:
- Sentosa SA Reporter;
- Sentosa SX Virus Total Nucleic Acid Kit;
- Sentosa SA HSV1/2 Qualitative PCR Test;
- Sentosa SX Safe-Lock Tubes;
- Sentosa SX Partition 50µL Filter Tips;
- Sentosa SX Partition 1000µL Filter Tips;
- Sentosa SX 100mL Reservoir;
- Sentosa SX 30mL Reservoir;
- Sentosa SX Deepwell Plates 96/2000µL
- Sentosa SX Rack for 96 1.5/2.0mL Screw Tubes;
- Sentosa SX Microplates 96/V;
- Sentosa SX Biohazard Bag;
- Sentosa SX PCR Foil, adhesive;
- Sentosa SX Thermoblock PCR 96;
- Sentosa SX Dispensing tool TM 50
- Sentosa SX Thermoblock PCR 96
- MicroAmp[®] Splash-free Support Base;
- MicroAmp[®] Fast Optical 96-Well Reaction Plate with Barcode, 0.1 mL;
- MicroAmp[®] Optical Adhesive Film.

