6.4 Data collection and submission, and record keeping

6.4.1 Data collection and submission

Data collection will be electronic print-outs or files from laboratory instruments, and electronically or manually completed data collection instruments. Data collection instruments will be completed at the time of sample collection and will be sent electronically, if completed electronically, or by fax and/or courier (e.g., FedEx, UPS, or USPS) as agreed between the clinical site and the study manager, if completed manually. Electronic print-outs or files may be faxed or transmitted electronically to the sponsor or designee daily when testing is completed, as requested. Signed copies of the test data and any electronically or manually completed data reporting forms will be submitted via courier to the data management group.

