7.3 Discrepant results

Extracted nucleic acids (20-30 uL) from samples that yield discordant results between the investigational and reference methods will be shipped to Vela Research USA and tested with different primers by PCR and bidirectional sequencing. If there is not sufficient sample for retesting, the discordances will be reported without further testing.

Discrepant testing results will not be used to generate sensitivity and specificity data, but will be reported as a footnote in the package insert.

8. Record and sample retention

All samples and records must be retained by the clinical investigator in condition suitable for inspection for the longest of:

- 2 years from the date of FDA clearance to market of the investigational device;
- 2 years following termination or completion of the entire clinical investigation; or
- record retention policy of the clinical site or associated IRB.

The clinical investigator will be notified by the sponsor of the date of marketing clearance or termination of the clinical investigation. Measures should be taken to prevent accidental destruction of documents and samples. Sample aliquots must be maintained at -70°C or below and at the end of all testing must be shipped to the sponsor.

9. Training

Good clinical and laboratory practices must be followed throughout the study. Instructions for use must be followed for all assay methods used in the study.

One or more individuals will be identified at each site to be responsible for all testing with the *Sentosa*[®] SA HSV1/2 Qualitative PCR Test. The sponsor will install the testing system and train laboratory personnel on the instruments prior to study initiation. Only individuals trained on the *Sentosa* SA HSV1/2 Qualitative PCR Test are qualified to test samples for this study.

System maintenance as described in Operating Manuals and during training must be done. Maintenance forms will be provided and must be completed as required.

10. Regulatory Considerations

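### Discordant samples are retested by the sponsor's affiliate with no provision to withhold the two assay results; the concern is confined to the package-insert footnote

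*Combined protocol and SAP*

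**What the plan says.** Section 6.2.3 (Concordance): "Samples that yield discordant results between the investigational and reference methods will be re-tested by Vela Research USA". In Section 7.3 (Discrepant results) the material is a small volume (20 to 30 µL) of nucleic acid extract taken from the discordant samples, which "will be shipped to Vela Research USA and tested with different primers by PCR and bidirectional sequencing". Both sections limit the retest to samples with enough volume; under 7.3 the remaining discordances are reported as they stand. Section 7.3 also says that retest results do not enter sensitivity or specificity, "but will be reported as a footnote in the package insert".

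On who holds the results, Section 6.2.3 says: "Results will be sent to the study manager for review". Section 6.4.1 adds: "Electronic print-outs or files may be faxed or transmitted electronically to the sponsor or designee daily when testing is completed, as requested". Section 10.3 lets the monitor, who represents the sponsor, review both investigational and reference assay results.

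The named sponsor is Vela Research Singapore. Vela Research USA appears under the heading of Section 4.1 on sponsor-supplied materials ("Vela Research USA will supply the following reagents and equipment and its associated software to each testing site"), and the contact page gives it as the organisation of the sponsor's project manager. The contact page places the study manager at a separate consulting firm.

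**The concern.** Section 1.1 credits amplification methods with enhanced sensitivity, so some samples positive on the test assay and negative on the reference should be expected. The footnote is the only evidence in the plan on whether such samples contain HSV DNA. A reader of the package insert will use it for that purpose.

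The retest is done by a party with an interest in the answer. It receives only disputed samples, and the plan does not say that the two assay results are withheld from it. If the laboratory knows which assay was positive, decisions that need judgement, such as whether to repeat a reaction or how to call a weak sequence, could lean one way. The documents give no rule for such decisions. What is at stake is how much weight the footnote can bear, not the main performance estimates.

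**Working it through.** The plan states no figure on this point, so the check is a comparison of sections.

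1. **What is retested.** Sections 6.2.3 and 7.3 both name discordant samples. No section retests a concordant sample. The laboratory therefore knows that every item it receives is disputed, whatever else it is told.

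2. **Masking.** The only blinding statement in the documents covers the precision panel in Section 6.2.2. Sections 6.2.3, 7.3, 6.4.1 and 10.3 contain none for the retest.

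3. **Access.** Sections 6.4.1 and 10.3 permit results to reach the sponsor side. They do not say that the retesting bench receives them.

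4. **Linkage.** Section 5.3 labels each sample with a site-and-sequence study ID, and Section 10.2 identifies all information by that ID. No new code is planned for shipment. Material sent under its study ID could be matched to the result files by anyone who holds both.

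5. **Reach.** In Table 1 of Section 7.2, sensitivity is a/(a+e+m) and specificity is f/(b+f+n). No retest result enters any cell. The equivalence rule (above 92.5% and 93.6% for both viruses at two or more of three sites) uses only these quantities, so it cannot change.

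6. **Size.** An estimate would need the number of discordant samples, their split between cells b and e, and the difference between masked and unmasked calls. The documents give none of these. The acceptance limit does not supply them: at a specificity of 93.6%, (b+n)/(b+f+n) = 1 − 0.936 = 6.4%. That total includes test-invalid results (n), so it is only a ceiling on b/(b+f+n), and the number of reference-negatives is not given.

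7. **What discordant-only selection does.** Suppose D of N samples are discordant, all are retested, and k retests side with the test assay. A reader who re-scores the table gets agreement of (N − D + k)/N. This can never fall below (N − D)/N, because no concordant pair can be overturned. Take N = 585 + 495 = 1080, assume discordance of 2%, 5% or 10%, and assume an uninformative retest (k = D/2):
   - D = 22, k = 11: agreement goes from 98.0% to 99.0%.
   - D = 54, k = 27: from 95.0% to 97.5%.
   - D = 108, k = 54: from 90.0% to 95.0%.

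   The discordance rates are assumptions. The shift comes from the selection and would arise under full masking too, so it does not measure the effect of missing masking. It shows why the footnote should not be used to re-score the table.

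8. **Material.** Section 6.2.3 speaks of retesting samples, Section 7.3 of shipping extracted nucleic acid. If the extract is the one from the test assay's own run, the retest would share any contamination introduced at extraction. The two sections need to be reconciled.

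**The case against.** The plan already takes the main precaution: Section 7.3 keeps retest results out of sensitivity and specificity, so harm requires a reader to do a recalculation that the plan itself declines to do. Different primers with bidirectional sequencing give a fairly objective readout that leaves limited room for preference. Both arguments stand, and they make this a modest point.

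A reader might also infer that the retest is known to be unmasked. The documents do not support that. They are silent on masking, results go to a study manager outside the sponsor's organisation, and the sentence in Section 6.4.1 is permissive, covers print-outs or files, and does not say that reference results travel that way. Section 10.3 does give the monitor sight of both assays, but that does not put them in front of the laboratory. The supportable statement is that masking is not specified.

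What the objection does not remove is that discordant status is known from the selection alone, that nothing prevents the laboratory from learning the direction, and that the result is published.

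**Conclusion.** The concern holds in a limited form. An affiliate of the sponsor retests discordant samples only, no provision masks it to the two assay results, and the sponsor side is allowed to see results. The planned estimates, their intervals and the equivalence decision are unaffected.

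Only the package-insert footnote is exposed, to an extent that the documents do not allow one to estimate and that the retest method limits. A reader might be tempted to size it by moving confirmed samples out of the reference-negatives at the specificity limit. That would need an assumed number of reference-negatives and an arbitrary confirmation rate, and would still not compare masked with unmasked retesting.

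The conclusion assumes that no masking procedure exists in a document not included here.

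**What to change.** In Sections 6.2.3 and 7.3, state that:

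- the study manager, who already receives the results, recodes the retest material and holds the key;
- the retesting laboratory receives neither assay's result nor the direction of discordance until its calls are locked;
- the footnote reports retest results separately for each direction of discordance, together with the number not retested.

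The cost is a recoding step. Recoding hides the direction of discordance, but discordant status itself stays known.

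Optionally, mix in a small random set of concordant-positive and concordant-negative specimens of the same material type and report their retest results alongside. This would hide discordant status and give a background rate for the retest. Whether the retest uses residual sample (6.2.3) or extracted nucleic acid (7.3) must be settled beforehand. The leftovers that Section 6.2.3 already sends to the affiliate ("Any sample left after all testing is completed should be frozen") are sample, not extract, so they would not match discordant extracts. The option costs extra PCR and sequencing reactions and, if extracts are used, retention of concordant extracts, for which the plan makes no provision.

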6.3 Test procedure

Refer to the *Sentosa*[®] SX101 System Instrument User's Manual for specific instructions for operating and maintaining the components of the system. The optimum environmental conditions for the *Sentosa* SX101 are 18°C - 27°C and 20 – 85% relative humidity.

6.3.1 Sample processing procedure

Sample material present on a swab will be eluted by vigorous agitation (i.e., vortexing) of the transport tube. The swab should then be discarded as biohazardous waste. Only clear sample eluent may be used as inoculum. If visual precipitates are observed, the eluent should be centrifuged at 4000 rpm for 10 minutes; the clear supernatant should be collected as inoculum. If centrifugation does not exclude precipitate the sample will be considered contaminated.

All frozen samples (sample eluent) must be allowed to thaw completely at room temperature and must be mixed by inversion.

During the procedure 250 µL of sample is transferred into a fresh 1.5 mL *Sentosa*[®] SX Safe-Lock Tube with proper label, in a biosafety cabinet, for sample loading of *Sentosa* SA HSV1/2 Qualitative PCR Test.

6.3.2 Procedure of Sentosa SA HSV1/2 Qualitative PCR Test.

Refer to the reference user manual of *Sentosa* SA HSV1/2 Qualitative PCR Test for detailed work instructions.

6.3.3 Control values for valid results

For the test to be valid, the negative control must be negative for fluorescence channels cycling green and cycling orange and positive for fluorescence channel cycling red, and the positive control must be positive for fluorescence channels cycling green and cycling orange

Results interpretation

For Negative control

	Negative control (N	Interpretation		
Green	Orange	Red*	Interpretation	
-	-	+	Proceed to PC	
+	-	+/-		
-	+	+/-	Run invalid	
+	+	+/-		
-	-	-	Run invalid	

For Positive control

	Positive control (PC	Interpretation		
Green	Orange	Red*	Interpretation	
+	+	+/-	Proceed to Samples*	
+	-	+/-		
-	+	+/-	Run invalid	
-	-	+/-		

For Samples

Samples			la to wave to tion
Green	Orange	Red*	Interpretation
-	-	+	HSV1 and HSV2 DNA not detected, extraction control positive
-	+	+/-	HSV2 DNA detected*
+	-	+/-	HSV1 DNA detected*
+	+	+/-	HSV1 and HSV2 DNA detected*
-	-	-	Sample invalid

^{*}Fluorescence channel Cycling Red can be negative due to competition with target channels.

6.3.4 Retest Criteria

If results of any test run are invalid due to failure of a positive or negative control failure, or if instrument specifications such as temperature or humidity conditions are out of specification, repeat testing will be performed.

Other conditions that require repeat testing include:

- machine failure;
- presence of an error message or flag in the machine;
- wrong sample tested;
- sample invalid status;
- wrong assay or extraction kits used;
- procedure error occurred; and

testing protocol was not followed.

6.4 Data collection and submission, and record keeping

6.4.1 Data collection and submission

Data collection will be electronic print-outs or files from laboratory instruments, and electronically or manually completed data collection instruments. Data collection instruments will be completed at the time of sample collection and will be sent electronically, if completed electronically, or by fax and/or courier (e.g., FedEx, UPS, or USPS) as agreed between the clinical site and the study manager, if completed manually. Electronic print-outs or files may be faxed or transmitted electronically to the sponsor or designee daily when testing is completed, as requested. Signed copies of the test data and any electronically or manually completed data reporting forms will be submitted via courier to the data management group.

6.4.2 Study document maintenance

Clinical study conduct must be documented. Training in study document maintenance will be done at the time of trial initiation at each clinical site. General instructions include the following:

- forms completed manually must be done in blue or black ink;
- fields must never be left blank if information is not available or not applicable this must be noted:
- changes or corrections to documents are done by a single line strike through the incorrect information, with the corrected information initialled and dated by the person making the correction *under no circumstances may white-out be used, the original entry must not be obscured;*
- copies of all records will be sent to the sponsor or designee as requested, original records will be kept at the clinical site;
- responsibility for ensuring accuracy, legibility, completeness, and timeliness of data lies with the clinical investigator;
- study document binders and forms will be supplied by the sponsor.

7. Statistical considerations

7.1 Sample size justification

A minimum of 585 oral samples and 495 genital samples will be collected and tested.

The clinical sample set may be enriched with contrived positive samples where virus is spiked into either negative clinical matrix or VTM.

A minimum of 73 samples per analysis group guarantees that at a minimal acceptable concordance of 95% (positive or negative) the lower bound of the 95% binomial confidence interval will be greater than 90%.

7.3 Discrepant results

Extracted nucleic acids (20-30 uL) from samples that yield discordant results between the investigational and reference methods will be shipped to Vela Research USA and tested with different primers by PCR and bidirectional sequencing. If there is not sufficient sample for retesting, the discordances will be reported without further testing.

Discrepant testing results will not be used to generate sensitivity and specificity data, but will be reported as a footnote in the package insert.

8. Record and sample retention

All samples and records must be retained by the clinical investigator in condition suitable for inspection for the longest of:

- 2 years from the date of FDA clearance to market of the investigational device;
- 2 years following termination or completion of the entire clinical investigation; or
- record retention policy of the clinical site or associated IRB.

The clinical investigator will be notified by the sponsor of the date of marketing clearance or termination of the clinical investigation. Measures should be taken to prevent accidental destruction of documents and samples. Sample aliquots must be maintained at -70°C or below and at the end of all testing must be shipped to the sponsor.

9. Training

Good clinical and laboratory practices must be followed throughout the study. Instructions for use must be followed for all assay methods used in the study.

One or more individuals will be identified at each site to be responsible for all testing with the *Sentosa*[®] SA HSV1/2 Qualitative PCR Test. The sponsor will install the testing system and train laboratory personnel on the instruments prior to study initiation. Only individuals trained on the *Sentosa* SA HSV1/2 Qualitative PCR Test are qualified to test samples for this study.

System maintenance as described in Operating Manuals and during training must be done. Maintenance forms will be provided and must be completed as required.

10. Regulatory Considerations

10.1 Institutional Review Board (IRB) review

This protocol and all other applicable documents will be submitted to the IRB at each participating clinical site for review and approval. The clinical investigator at each site shall obtain written confirmation from the IRB that the protocol and other applicable

documents have been approved. The study cannot commence at a clinical site until IRB approval is received.

If the clinical study extends beyond the approved time period, the clinical investigator will request renewal of the IRB approval to conduct the study. The renewal application must include all applicable documents required for the duration of the study. Written confirmation that the study approval has been renewed must be obtained from the IRB.

The clinical investigator will inform the IRB when the study is terminated and obtain written confirmation from the IRB of study closure.

